- with a GCS ≤ 8 , who have no evidence of a TBI and have a blood alcohol level above the legal limit in the state of Virginia (0.8 or higher).
- with a known diagnosis of dementia prior to admission; patients who dislike or are allergic to dogs
- under isolation precautions with the exception of neutropenic precautions for any reason, including MRSA, C Diff, or VRE.
- unable to speak Spanish or English.
- those who would have religious/cultural reasons for avoidance of dogs
- patients who have a splenectomy

Study Methodology: Patients meeting study criteria will be enrolled in the study and randomized into either the intervention or control group. Those randomized into the intervention group will receive the animal-assisted therapy up to three times weekly, in addition to their usual care. Those randomized into the control group will receive standard of care.

Statistical Methods

Aim 1: The primary outcome for analysis will be the difference in Rancho Los Amigos Scale (RLAS) scores from pre-intervention to post-intervention (Δ RLAS). Weekly Δ RLAS will be compared between the AAT group and controls using nonparametric Wilcoxon rank sum tests (Mann-Whitney U tests). This analysis will be stratified by weeks 1-4 to determine whether the difference in Δ RLAS between AAT and controls changes over time.

Aim 2: The outcome for analysis will be the difference in Level of Commands (LOCmds) and Glasgow Coma Scale (GCS) and movement of extremities from pre-intervention to during-intervention and will be analyzed using the same methodology as in Aim 2.

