4. AAT and measurements of the same data will continue up to three times weekly after the initial measurements and will be listed on data collection sheets. If the patient is unavailable for AAT at the time of the scheduled intervention, the research team will document "unavailable," indicate the reason for unavailability. The patient will remain in the study and data collection will continue until the patient is discharged, reaches RLAS 7, or have been hospitalized ≥ 28 days. If the patient has been discharged from the study but remains in the hospital, he/she may continue to receive AAT.

Control Group

1. When the patient is randomized to the control arm, data measurements will be taken by the bedside RN. Variables to be collected include:
 - A. RLAS Score
 - B. GCS Score
 - C. Level of Command-0, 1 or 2 or 3-step (see same data collection sheet).
 - D. Movement of Extremities
2. The control group will be receiving standard of care bedside interventions. During the control measurement period, the only person present will be the bedside nurse who records the measurements. RLAS, GCS, and Level of Command and movement of extremities will be measured by the same licensed healthcare professional before and after each interaction with the healthcare professional.
3. The PI will be responsible for collecting measurements of the same data up to three times weekly after the initial measurements until they are discharged, reach RLAS 7, or have been hospitalized ≥ 28 days.

When the subject is moved to a different unit, study personnel will continue to be responsible for ensuring the study measurements, as measured by the bedside nurse, are recorded on the data collection form.

Methods for Tracking Recruitment and Retention. Study personnel will:

- Screen the trauma services database to determine the number of patients appropriate for the study.
- Keep detailed notes regarding the number of patients identified as potential participants by the study personnel to determine the percentage of eligible patients approached for inclusion into the study to determine the efficacy of our program to treat this population

- Keep detailed logs reflecting the number of patients approached to participate and the reasons for declining participation and for loss to follow up to determine the willingness of participants to consent to participate and remain in the study.

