4. STATISTICAL CONSIDERATIONS/DATA ANALYSIS

4.1. Sample Size: We estimate that approximately 85% of the patients with TBI will consent for this study. In consideration of the study's endpoints, it is expected that approximately 50 patients will be in each of the two study groups.

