4.2. Method of Data Analysis

Aim 1: To determine if the use of animal assisted therapy in the plan of treatment of patients with TBI results in higher scores on the Ranchos Los Amigos, Glasgow Coma Scale, an increased ability to follow commands, and an increased movement of extremities than those who do not receive AAT.

The difference in RLAS scores from pre-intervention to post the intervention will be the primary outcome for the analysis. The outcome, Δ RLAS, will be defined as RLAS during AAT/sham – RLAS pre-AAT/sham. Δ RLAS from each study visit (AAT or sham) will be averaged over each week of the study (weeks 1-4). To address the primary hypothesis, weekly Δ RLAS will be compared between the AAT group and controls using nonparametric Wilcoxon rank sum tests (Mann-Whitney U tests) in order to determine whether the AAT group has significantly higher Δ RLAS. This analysis will be stratified by weeks 1-4 to determine whether the difference in Δ RLAS between AAT and controls changes over time.

The difference in LOCmd scores and movement of extremities will be a secondary outcome of this study. Δ LOCmds and movement of extremities will be defined similarly to Δ RLAS, as the LOCmds and movement of extremities during AAT/sham – LOCmds and movement of extremities pre-AAT/sham, and the mean Δ LOCmds and movement of extremities will be calculated for each week of the intervention (1-4). Weekly

Δ LOCmd scores and movement of extremities will be compared between study groups (AAT vs. controls) using nonparametric Wilcoxon rank sum tests. This analysis will be stratified by weeks 1-4 to determine whether the difference in Δ LOCmd and movement of extremities between AAT and controls changes over time.

GCS scores are routinely collected every hour by the TICU nursing staff. Medical charts will be reviewed to record the GCS scores during the hour immediately before and immediately after the intervention (or sham) is implemented. Δ GCS will be defined as GCS after AAT/sham – GCS pre-AAT/sham. Weekly Δ GCS scores will be compared between study groups (AAT vs. controls) using nonparametric Wilcoxon rank sum tests. This analysis will be stratified by weeks 1-4 to determine whether the difference in Δ GCS between AAT and controls changes over time.

Aim 2: To determine if the use of animal assisted therapy in the plan of treatment of patients with TBI are discharged with a higher degree of cognitive function than those who did not receive AAT.

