To address the primary hypothesis, weekly Δ RLAS will be compared between the AAT group and controls using nonparametric Wilcoxon rank sum tests (Mann-Whitney U tests) in order to determine whether the AAT group has significantly higher Δ RLAS. This analysis will be stratified by weeks 1-4 to determine whether the difference in Δ RLAS between AAT and controls changes over time.

The difference in LOCmd scores will be a secondary outcome of this study. Δ LOCmd and movement in extremities will be defined similarly to Δ RLAS, as the LOCmds and movement of extremities during AAT/sham – LOCmds and movement of extremities pre-AAT/sham, and the mean Δ LOCmds and movement of extremities will be calculated for each week of the intervention (1-4). Weekly Δ LOCmd scores and movement of extremities will be compared between study groups (AAT vs. controls) using nonparametric Wilcoxon rank sum tests. This analysis will be stratified by weeks 1-4 to determine whether the difference in Δ LOCmds and movement of extremities between AAT and controls changes over time.

4.3. Data Storage: The data will be stored on a password protected computer in the AAC office for three years in a Microsoft Excel 2010 database and then destroyed. Only study personnel will have access to these data.

4.3.1. Data Management: Information about study subjects will be kept confidential and managed according to the requirements of the Health Insurance Portability and Accountability Act of 1996 (HIPAA). Privacy and confidentiality of all enrolled patients will be maintained. All data collection tools will be taken to the AAC Office and will be entered by LH into the secure study data base. Consent documents and the regulatory binder will be kept in the Trauma Research Manager's office. The Trauma Department suite is locked, and the Trauma Research Manager's office is locked.

4.3.2. Records Retention: The data will be stored for three years in a Microsoft Excel 2010 database and then destroyed.

5. HUMAN SUBJECTS PROTECTION (RISKS, BENEFITS, and ALTERNATIVES)

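### Four weekly Wilcoxon tests serve one primary hypothesis with none named as deciding, and the split by week cannot show whether the effect changes over time

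*Protocol*

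**What the plan says.** Protocol section 4.2, Aim 1, defines the outcome within each visit: "The outcome, Δ RLAS, will be defined as RLAS during AAT/sham – RLAS pre-AAT/sham". Visits are then reduced to one value per patient per week: "Δ RLAS from each study visit (AAT or sham) will be averaged over each week of the study (weeks 1-4").

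The test follows: "To address the primary hypothesis, weekly Δ RLAS will be compared between the AAT group and controls using nonparametric Wilcoxon rank sum tests", with a directional purpose, "in order to determine whether the AAT group has significantly higher Δ RLAS". The next sentence gives the weekly split a second job: "This analysis will be stratified by weeks 1-4 to determine whether the difference in Δ RLAS between AAT and controls changes over time".

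The same scheme appears under Aim 2 in section 4.2 and in the abstract's Statistical Methods. It is also applied to level of commands, movement of extremities and, under Aim 1, GCS.

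Hypothesis 1 in section 1.2 is a single claim and singles out no week. Nothing in the protocol defines a summary across weeks, a deciding week, a rule for combining the weekly results, or an interaction or repeated-measures test.

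Follow-up length varies by patient. Section 3 says "data collection will continue until the patient is discharged, reaches RLAS 7, or have been hospitalized" for 28 days or more, and section 3.4 lists the same end points. On size, section 4.1 says only that "it is expected that approximately 50 patients will be in each of the two study groups".

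**The concern.** There are two separate defects.

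1. **No deciding comparison.** One hypothesis receives up to four p-values, and the text does not say which decides. A chance finding in one week could be presented as success. A trial with one significant week and three non-significant ones has no defined conclusion.

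2. **The wrong tool for change over time.** A significant week 1 beside a non-significant week 4 does not show that the arm difference changed. The two differences have to be compared with each other, allowing for the fact that the same patients contribute to both. The stopping rules make this worse: patients leave at discharge or RLAS 7, so later weeks compare fewer and different patients. A constant effect loses significance for that reason alone.

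Reading *stratified* as one pooled, week-stratified rank test does not help. Such a test does not assess change over time. It also treats a patient's weekly values as independent across strata, which inflates its error rate when those values are positively correlated.

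**Working it through.** **Inputs from the protocol:** four weekly comparisons (4.2); about 50 per group (2.4, 4.1); 1:1 allocation (3.3); data collection ending at discharge, RLAS 7 or 28 days (3, 3.4). The figure of 50 per group cannot be reproduced, because no alpha, power, effect size or SD is given.

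**Assumptions, none of them in the protocol:** two-sided 0.05 per test; success if any week is significant; within-patient correlation r of 0 to 0.9; an effect of 0.5 SD where one is needed; per-arm numbers either 50 every week or 50/40/30/20, with departure unrelated to outcome.

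**Step 1. Any-week false positives, independent weeks.** 1 − 0.95⁴ = 1 − 0.8145 = 0.185. If each test were one-sided at 0.025: 1 − 0.975⁴ = 0.096.

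**Step 2. False positives with correlated weeks.** Simulation under no effect, 6,000 trials per setting, normal weekly ΔRLAS, per cent:

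| Analysis | Numbers per arm | r=0 | 0.3 | 0.5 | 0.7 | 0.9 |
|---|---|---|---|---|---|---|
| Any of four weekly tests | 50 each week | 18.2 | 18.4 | 15.5 | 13.9 | 10.0 |
| Any of four weekly tests | 50/40/30/20 | 17.9 | 17.4 | 16.4 | 15.6 | 13.0 |
| One pooled week-stratified test | 50 each week | 4.8 | 15.7 | 21.1 | 27.0 | 31.7 |
| One pooled week-stratified test | 50/40/30/20 | 4.4 | 12.6 | 18.0 | 22.9 | 26.4 |

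One Wilcoxon test on each patient's mean gave 4.6–5.4% across all ten settings.

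**Step 3. Apparent change when there is none.** With a constant 0.5 SD effect, the share of trials in which some weeks are significant and others are not was:

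| Numbers per arm | r=0.3 | 0.5 | 0.7 |
|---|---|---|---|
| 50 each week | 65% | 55% | 42% |
| 50/40/30/20 | 80% | 73% | 64% |

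At r = 0.5 with falling numbers, simulated weekly power was 68/58/46/31%. A normal approximation gives the same pattern. Power is Φ(d√(n/2) − 1.96):
- n = 50: Φ(0.5 × 5 − 1.96) = Φ(0.54), about 70%.
- n = 20: Φ(0.5 × 3.162 − 1.96) = Φ(−0.38), about 35%.

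The true effect is identical in every week; only the numbers differ. In these constant-effect trials a linear arm-by-week term with patient-clustered robust standard errors wrongly signalled change in 5.0–5.6%.

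**Step 4. Does normality matter?** RLAS changes will be heavily tied.
- With discrete visit changes of −1, 0 or +1 (mostly 0, three visits weekly), any-week false positives were 10–18%, and the patient-mean test ran at 4.4–5.3%. Under a constant shift at r = 0.5, mixed results occurred in 48% (full numbers) and 69% (falling numbers).
- With a binary visit-level change at event rates of 5% or 20%, the any-week error was 13–19% and the patient-mean test 4–6%.

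**Step 5. Power of a single test.** At r = 0.5 and 0.5 SD, the Wilcoxon on per-patient means had 86% power with full numbers and 81% with falling numbers.

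**The case against.** The best counter-argument is that alpha, sidedness and multiplicity control commonly belong in an analysis plan, and this trial's plan is not at hand. That is right for multiplicity detail. It does not cover what the protocol itself fixes: weekly comparisons as the analysis of the primary hypothesis, and the weekly split as the means of judging change over time.

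The text might also mean an overall comparison followed by a weekly breakdown. No overall per-patient summary is defined, however, so that reading is not written down either.

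The figures are conditional. The 18.5% needs two-sided 0.05 and an any-week rule; a one-sided 0.025 level gives 9.6%, and requiring every week to be significant would give no inflation. The mixed-result shares assume that change is judged by comparing significance. Only non-negative correlations were simulated, and the pooled test's inflation needs positive correlation. The simulated departures ignore outcome, whereas the protocol ends data collection at RLAS 7, so the error rates near 5% do not cover that feature. All of this stands as a limit on the percentages, not on the two defects.

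Section 2.5.3 calls the study a pilot, which could argue for a milder view. But the protocol still sets out to test a primary hypothesis, and as written that test has no single answer.

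**Conclusion.** The concern holds and should be corrected before analysis. The protocol gives one primary hypothesis up to four results without naming a deciding one, and it assigns the weekly split a question that neither separate nor pooled rank sum tests can answer.

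Under the assumed any-week rule at two-sided 0.05, the false-positive risk is about 10–18% for correlation 0.9 to 0.3, instead of 5%. Read as one pooled week-stratified test, it is about 13–32% for correlation 0.3 to 0.9, with no inflation at zero. With a constant 0.5 SD effect, weekly results disagree in 42–65% of trials at full numbers and 64–80% with falling numbers, for correlation 0.7 to 0.3. The exact sizes depend on assumptions that the protocol does not supply; the two defects do not.

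**What to change.** In section 4.2 and the abstract:

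- **Primary analysis:** one two-sided 0.05 Wilcoxon rank sum test on each patient's mean ΔRLAS over all visits, one value per patient.
- **Change over time:** an arm-by-week term in one repeated-measures model of weekly ΔRLAS that accounts for within-patient correlation, for example a linear week trend with patient-clustered robust standard errors, as simulated. Interpret it with caution, because leaving the study depends on outcome.
- **Weekly comparisons:** report all four as descriptive.
- **Level of commands, movement of extremities and GCS:** keep outside the primary test.

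The cost is wording and one added model, with no extra data or change in conduct. There are three downsides: a single significant week no longer counts as success, patients' means rest on differing numbers of visits, and the arm-by-week result stays exposed to outcome-dependent departure.

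Naming one week as primary would also supply a deciding comparison. Keeping all four tests with Bonferroni at 0.05/4 = 0.0125 would control the error, but at a price. At 50 per arm the difference detectable with 80% power in one week rises from 0.56 SD to 0.67 SD (normal approximation), and 72 per arm would be needed to recover 80% power for 0.56 SD. Neither alternative tests change over time.

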1. INTRODUCTION

1.1 .Specific Aims

Aim 1: To determine if the use of animal assisted therapy in the plan of treatment of patients with TBI results in differences in scores on the Ranchos Los Amigos Scale, Glasgow Coma Scale, and in an increased ability to follow commands from those who do not receive AAT.

Aim 2: To determine if the use of animal assisted therapy in the plan of treatment of patients with TBI are discharged with a different degree of cognitive function than those who did not receive AAT.

1.2 .Hypothesis

Hypothesis 1 Patients sustaining TBI who participate in AAT will experience a faster and higher elevation in RLAS, GCS scales and the ability to follow commands than those TBI patients who do not receive AAT.

Hypothesis 2 Patients sustaining TBI who participate in AAT will experience a faster and higher elevation in cognitive function (as evidenced by the ability to follow multiple commands) than those TBI patients who do not receive AAT.

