3.4. Endpoints/Outcome Measures

Patients enrolled in the study will participate until any of the following occurs:

1. choose to no longer participate
2. develop animal allergies
3. reach a RLAS of 7 or above
4. are discharged
5. are hospitalized for greater than or equal to 28 days.

3.5. Consent/Assent: Informed consent will be obtained by the PI or TICU RNs who are sub-investigators on the study. Patients or legally authorized representative of potential subjects will give consent. Patients who do not speak English or Spanish will not be consented.

3.6. Monitoring Subjects and Criteria for Withdrawal of Subjects from the Study.

Criteria for withdrawing subjects from the study are at patient and/or patient LAR request.

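### Aim 2 asks about cognitive function at discharge, but its stated analysis only repeats Aim 1's weekly tests of within-session change

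*Protocol*

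**What the plan says.** **The question.** Protocol section 1.1 asks whether patients given AAT "are discharged with a different degree of cognitive function than those who did not receive AAT". Section 4.2 restates the aim as whether they "are discharged with a higher degree of cognitive function than those who did not receive AAT". The direction differs, but both refer to a level of function at discharge.

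**The hypothesis.** Hypothesis 2 in section 1.2 predicts a faster and higher "elevation in cognitive function (as evidenced by the ability to follow multiple commands"). It does not mention discharge.

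**The analysis.** Under Aim 2 in section 4.2, the RLAS paragraph opens "To address the primary hypothesis, weekly" Δ RLAS, and its two sentences are word for word those used for Aim 1. The next paragraph begins "The difference in LOCmd scores will be a secondary outcome of this study" and defines Δ LOCmd and Δ movement as the score during the session minus the score before it, averaged by week. Every comparison is a Wilcoxon rank sum test for weeks 1 to 4.

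**The abstract.** Its Aim 2 outcome is LOCmd, GCS and "movement of extremities from pre-intervention to during-intervention and will be analyzed using the same methodology as in Aim 2". That is again a pre-to-during change, the set of measures differs from section 4.2, and the method reference points to itself.

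**Data collection.** Section 3 says that "data collection will continue until the patient is discharged, reaches RLAS 7" or has been in hospital for 28 days or more. Section 3.4, headed as endpoints and outcome measures, lists only reasons for leaving the study, among them that patients "reach a RLAS of 7 or above".

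**The concern.** Function at discharge is a level reached at a point in time. The planned tests measure how much a patient's score moves while a session is under way. These are different quantities, and the protocol does not argue that one stands in for the other. The repeated sentences, including the reference to the primary hypothesis, suggest text carried over from Aim 1 rather than a chosen surrogate.

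Two things are at stake. One of the protocol's two aims would get no answer. And a significant result from these tests, sitting under a heading about discharge, could be reported as better function at discharge when it shows only an immediate response. If a discharge comparison were added after the data had been seen, its measure, time point and handling of deaths would all be post hoc choices.

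**Working it through.** No figure in the protocol is in dispute here, so the check is a count, an identity and a worked case. The power of the proposed replacement follows.

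**1. Count of stated tests (section 4.2)**
- Aim 1: RLAS, LOCmd, movement and GCS, each in 4 weeks: 4 × 4 = 16.
- Aim 2: RLAS, LOCmd and movement, each in 4 weeks: 3 × 4 = 12, all of them among the 16.
- Distinct tests across both aims: 16.
- Tests using a discharge score, a last score or a change since enrolment: 0.

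**2. What within-session change leaves out**

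Write P(k) for the score before session k and D(k) for the score during it. With K sessions,

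P(K) − P(1) = Σ [D(k) − P(k)] + Σ [P(k+1) − D(k)], both sums over k = 1 to K − 1.

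The planned tests use terms of the first kind only. Section 3 allows up to three sessions a week, so four weeks give at most 3 × 4 = 12 sessions. That means 12 within-session changes, all used, and 11 between-session changes, none used. Twelve is a ceiling, because the 28 days count time in hospital and sessions start only after enrolment.

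**3. Worked case on LOCmd (0 to 3), 12 sessions**

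| | Patient A | Patient B |
|---|---|---|
| Course | Rises from 0 to 2, both steps between sessions | Rises from 0 to 1 in each session, then falls back |
| Weekly mean Δ, weeks 1 to 4 | 0, 0, 0, 0 | 1, 1, 1, 1 |
| Last pre-session score | 2 | 0 |
| Last score of any kind | 2 | 1 |

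The planned tests rank B above A in all four weeks. The level reached ranks A above B on either definition of the last score. This follows from how Δ is defined and needs no assumed treatment effect.

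**4. Power of the replacement comparison**

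Inputs: about 50 per arm (sections 2.4 and 4.1). The protocol gives no significance level, power or LOCmd distribution, so two-sided 5%, 80% power and four control distributions are assumed. Whitehead's formula for ordered categories with equal arms, total N = 100, is

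log OR = √{12 × (1.960 + 0.842)² / [N × (1 − Σp̄³)]}, with (1.960 + 0.842)² ≈ 7.849,

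where p̄ is the mean of the two arms' proportions at each level. It is solved by iteration, because p̄ depends on the odds ratio.

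| Assumed control % at levels 0/1/2/3 | Σp̄³ | log OR | Detectable OR |
|---|---|---|---|
| 25/25/25/25 | 0.079 | 1.011 | 2.75 |
| 50/20/20/10 | 0.085 | 1.014 | 2.76 |
| 70/10/10/10 | 0.196 | 1.082 | 2.95 |
| 10/10/20/60 | 0.374 | 1.227 | 3.41 |

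First row: √[94.19 / (100 × 0.921)] = 1.011, and exp(1.011) = 2.75. With 40 per arm the same formula gives 3.1 to 4.0.

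**The case against.** **Only a secondary matter.** The primary outcome is within-session change in RLAS, and neither its definition nor its test is touched. No data are lost, since scores are recorded until the patient leaves the study. This is right, and it limits the point. A reader might infer that the primary analysis is invalid or that the trial cannot answer Aim 2; the protocol supports neither. What stands is that one of two stated aims has an analysis that does not address it.

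**A separate SAP may supply it.** This would be a good answer if the protocol left the Aim 2 analysis open. It does not: section 4.2 states one, and that one answers a different question.

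**The choice of LOCmd.** A reader might infer that Hypothesis 2 defines discharge function as LOCmd. It does not mention discharge, it speaks of a faster as well as a higher rise, and a single last score would not test speed. Section 4.2 lists RLAS first under Aim 2, while the abstract's Aim 2 omits RLAS. LOCmd is therefore a reasoned suggestion, resting on the link that Hypothesis 2 makes between cognitive function and following commands; the protocol does not require it.

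**A last score is imperfect.** This also stands. If AAT produces brief in-session rises, more AAT patients may touch RLAS 7 and leave early. Counting the score that ended participation then credits a rise that may fade. Using only the last pre-session score instead loses those patients' later recovery. Neither version is fully neutral between arms.

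**Conclusion.** The mismatch is established from the text. Aim 2 asks about function at discharge, all 12 tests listed for it duplicate Aim 1, and none of the 16 distinct tests uses a discharge or last score. Carried out exactly as written, the plan does not answer Aim 2. The abstract does not repair this: it too uses a pre-to-during change, names a different set of measures and cites its own method.

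That the two quantities can rank patients in opposite order rests only on the definition of Δ. How often this would happen, and whether it would alter the trial's conclusion, cannot be known from the protocol, and no such claim is made. The detectable odds ratios of about 2.8 to 3.4 depend on the assumed control distributions. They bear on how a null result should be read, not on whether Aim 2 needs its own analysis.

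**What to change.** **Change to section 4.2**
- Replace the duplicated Aim 2 text with one between-arm Wilcoxon rank sum comparison of the last in-study pre-session LOCmd score (in controls, the last pre-measurement score), defined identically in both arms. Give RLAS as supportive.
- As a sensitivity analysis, use the last recorded score of any kind, including the assessment that ended participation at RLAS 7.
- State in advance how deaths are ranked.
- State that the last score is a proxy for discharge function, because collection can stop at RLAS 7 or at 28 days in hospital, before discharge.
- Limit conclusions from within-session change to immediate response.

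**Change to the abstract.** Make its Aim 2 measures and method reference agree with section 4.2.

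**Alternative.** If no discharge comparison is adopted, reword Aim 2 wherever it appears so that it claims only immediate response.

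**Cost.** Wording and one added comparison on scores already collected; no new visits or measurements. The downsides are that the score is a proxy, that RLAS is capped near 7 by the exit rule, and that power is modest, so a non-significant result would not exclude a smaller difference.
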